6.6.9. Study group and treatment number allocation

Study group and treatment number allocation will be performed as described in Section 6.2.2. The number of each administered treatment must be recorded in the eCRF.

6.6.10. **Sampling**

Refer to the Module on Biospecimen Management in the Sponsor's SPM for detailed instructions for the collection, handling and processing of the samples.

6.6.10.1. Blood sampling for safety or immune response assessments

Blood samples will be taken during certain study visits as specified in Section 3 and Section 6.5. Refer to the SPM for details on samples handling, storage and shipment conditions.

• An overall volume of 400 mL will be collected per subject during the entire study period (8 months).

6.6.10.2. Urine sampling

- A urine sample for urinalysis should be collected from all subjects at each predefined timepoint, as per investigator's judgment.
- Urine samples for the pregnancy test will be collected from women of childbearing potential at each predefined timepoint (refer to Section 6.6.6).

6.6.10.3. Stool sampling

For the microbiome analysis, subjects will take a stool sample at home/at the hospital using the sampling material and instructions provided as close as possible to the study visit (preferably on the day of the visit). Immediately after stool sampling, participants will write down date and time of sampling and time since previous defecation and determine stool consistency using the Bristol Stool Score chart provided.

Aliquots of stool will be collected for fecal sIgA, inflammatory response, culture and qPCR, at each predefined timepoint (see Table 4). If, during the inpatient stay, no stools are passed on a given day, up to two rectal swabs can be collected for culture and qPCR (see also Section 3.2). The aliquots for fecal sIgA and inflammatory markers should be frozen at -80°C as soon as possible at the clinical site.

205626 (S SONNEI MONO GMMA SBVGH-003 [H03_03TP]) Protocol Amendment 6 Final

Refer to the SPM for more details on sample collection and storage conditions.

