Risks related to blood sample collection	When blood samples are taken from a vein, there is a risk of bruising at the site. There is a rare possibility of bleeding, fainting and infection or of nerve injury soreness.	Safe sampling procedures will be applied by appropriately trained and qualified staff to minimize distress and sampling errors. The potential risk of feeling faint, or experiencing mild local pain, bruising, irritation or redness at the site where blood was taken, is mentioned in the informed consent form. The amount of blood to be taken for sampling will not be harmful to the subject's health.							
Risk related to rectal swabs	Rectal swabs may cause discomfort for patients and in case of special conditions (e.g. hemorrhoids, and rectal polyps) bleeding might happen.	Rectal swabs are only collected when it is not possible to obtain a stool sample. Study staff will instruct the subjects on how to do the rectal swab.							
	Other (challenge phase)								
Severe and invasive diarrhea after challenge Risk of bacteremia after challenge	Illness caused by Shigella ranges from mild (watery diarrhea being the main symptom) to severe illness (fever and abdominal cramping with frequent small volume blood streaked stools containing mucus), dehydration and even shock. Perianal soreness, which is a skin irritation on your buttocks as a result of diarrhea, is possible. Bacteremia can occur with any invasive bacterial infection not appropriately contained with adequate antibacterial therapy.	Administration of an effective antibiotic will significantly reduce, or eliminate, symptoms within 24 hours of initiation. In addition, all challenged subjects will receive an effective antibiotic on the 5th day after challenge or earlier as required and intensive care unit is available to provide appropriate care in case of emergency. If perianal soreness occurs, it can be treated with topical lotion. The S. sonnei 53G challenge strain used in the challenge phase is known to be susceptible to multiple antimicrobial agents including Trimethoprim-Sulfamethoxazole (TMP-SMX) and quinolones which will be used in this study. To ensure there is no spread of shigella in the environment, subject will be discharged only following two							

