During the first 8 days in the inpatient unit (Day 57 to Day 64) following challenge, subjects will be monitored daily for AEs, gastrointestinal or other systemic signs and symptoms. Subjects will be assessed for vital signs (including sitting blood pressure, temperature and pulse rate) according to local standards for inpatient care. Stool analysis will be carried out daily during the inpatient stay. All stools will be collected and visually assessed for consistency, blood or mucus. Stools that are loose or watery (grades 3-5) will be weighed, and if there is visible blood, a Hemoccult test will be performed to confirm presence of occult blood. Up to two stools with blood present by visual inspection in a 24 hour period will be tested by Hemoccult. Study staff will record the information in the subject's source document. If a subject is unable to produce a stool by midnight, a rectal swab will be obtained (up to 2 adequately collected swabs per day). Study staff will record the information in the subject's source document. The first stool sample collected during a 24 hour period on the day after challenge agent administration (from 00:01 to 24:00) will be analyzed by culture and quantitative polymerase chain reaction (qPCR) specific for S. sonnei 53G. The day before discharge (Day 64), two stool samples will be collected to confirm that the subject is no longer shedding. Instructions for appropriate

205626 (S SONNEI MONO GMMA SBVGH-003 [H03_03TP])
Protocol Amendment 6 Final

collection, transportation and storage of stool samples will be provided to the investigators. For diarrhea episodes to be considered as separate episodes, there should be at least a 6-hour interval between them (refer to Section 4 for details on stool grading).

On the 5th day after challenge (Day 62), subjects will receive as first-line treatment 500 mg of ciprofloxacin twice daily for 3 days. Subjects with contraindication to ciprofloxacin may receive as second-line treatment trimethoprim-sulfamethoxazole (160 mg/800 mg twice daily), amoxicillin (500 mg three times daily) for 5 days, or any antibiotic that is deemed suitable according to local guidelines and the investigator's assessment can be used.

Subjects may be treated with antibiotics before the 5th day after challenge (Day 62) if:

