4.3. Shigellosis

For the primary and secondary objectives in the challenge phase of the study, the protocol primary case definition for shigellosis is:

• Shedding of *S. sonnei* 53G accompanied by moderate or severe diarrhea OR shedding with an oral temperature of ≥ 38.5 °C).

For the secondary objectives in the challenge phase of the study, 2 definitions of shigellosis are used:

- 1. CHIM working group case definition for shigellosis as defined by any one of the three following possible endpoints:
 - Severe diarrhea defined as [≥6 loose stools in 24 hours] OR [>800 grams loose stools in 24 hours]
 - Moderate diarrhea defined as [4-5 loose stools in 24 hours OR 400-800 grams loose stools in 24 hours] AND [oral temperature ≥38.0°C OR ≥1 moderate constitutional/enteric symptom OR ≥2 episodes of vomiting in 24 hours]
 - Dysentery defined as [≥2 loose stools with gross blood (hemoccult positive) in 24 hours] AND [oral temperature ≥38.0°C OR ≥1 moderate constitutional/enteric symptom OR ≥2 episodes of vomiting in 24 hours].
- 2. Shigellosis as defined by any one of the three following possible endpoints:
 - Severe diarrhea defined as [≥6 loose stools in 24 hours OR >800 grams loose stools in 24 hours]
 - Moderate diarrhea defined as [4-5 loose stools in 24 hours OR 400-800 grams loose stools in 24 hours] AND [oral temperature ≥38.0°C OR ≥1 moderate constitutional/enteric symptom].
 - Dysentery defined as [≥2 loose stools with gross blood (hemoccult positive) in 24 hours] AND [≥1 reportable constitutional/enteric symptom].

For the secondary objectives in the challenge phase of the study, more severe shigellosis is defined by any one of the two following possible endpoints:

- Moderate OR severe diarrhea [≥4 loose stools in 24 hours OR ≥400 grams loose stools in 24 hours] AND [oral temperature ≥38.0°C OR ≥1 severe constitutional/enteric symptom].
- Dysentery defined as [≥2 loose stools with gross blood (hemoccult positive) in 24 hours] AND [oral temperature ≥38.0°C OR ≥1 severe constitutional/enteric symptom]. (Amended: 23 July 2019)

205626 (S SONNEI MONO GMMA SBVGH-003 [H03_03TP])
Protocol Amendment 6 Final

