- ⁴ Sampling to be done 7 days after challenge agent administration (i.e., Day 64).
- ⁵ Additionally, hematology is repeated weekly until resolution if neutropenia occurs. On the day of vaccination/challenge, sampling will be done before vaccination/challenge.
- ⁶ Urine dipstick to be done for all subjects and, in case of abnormal results, a urine culture is to be performed (urinalysis).
- ⁷ Before vaccination/challenge (Day 1/Day 57 sample can be collected by the subject at most a week before and stored as described in the Investigator Manual and SPM.
- ⁸ Sampling to be done daily during inpatient stay and if subject is still shedding 7 days post-challenge administration (Day 64). However, all subjects even if not shedding anymore will remain in the inpatient stay until 7 days post-challenge and will be discharged on Day 65.
- ⁹ Samples collection can be performed between Day 56 and Day 57.

205626 (S SONNEI MONO GMMA SBVGH-003 [H03_03TP]) Protocol Amendment 6 Final

Whenever possible, the investigator should arrange study visits within the interval described in Table 5.

Table 5 Intervals between study visits (Amended: 23 July 2019)

Interval	Optimal length of interval	Allowed interval
Screening visit → Visit 1	-7 days	-45 days – -1 days
Visit 1 → Phone Call	3 days	2 days - 6 days
Visit 1 → Visit 2	7 days	7 days - 10 days
Visit 1 → Visit 3	28 days	26 days - 33 days
Visit $3 \rightarrow$ Phone call	3 days	2 days - 6 days
Visit 3 → Visit 4	7 days	7 days - 10 days
Visit 3 → Visit 5	28 days	26 days - 33 days
Visit 5 → Inpatient stay	9 days	9 days - as needed
Visit 5 → Visit 5 post-challenge blood draw (Amended: 23 July 2019)	7 days (Amended: 23 July 2019)	7 days – 10 days (Amended: 23 July 2019)
Visit 5 → Visit 6	28 days	28 days - 35 days
Visit 5 → Visit 7	56 days	49 days - 63 days
Visit 5 → Visit 8	180 days	166 days - 194 days

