11.2. Secondary endpoints

Efficacy

VE, in subjects receiving the 1790GAHB vaccine vs. placebo, will be also measured during inpatient stay (Day 57 to Day 64) against:

- Rate of shigellosis *as defined by* the CHIM working group case definition for shigellosis occurring within a period starting with challenge visit and lasting until the end of the inpatient stay, in all subjects. (*Amended: 23 July 2019*)
- Rate of shigellosis, as defined by: severe diarrhea OR moderate diarrhea with fever or with one or more moderate constitutional/enteric symptom OR dysentery [[≥2 loose stools with gross blood (hemoccult positive) in 24 hours] AND [≥1 reportable constitutional/enteric symptom]].
- Rate of more severe shigellosis as defined by: severe or moderate diarrhea with fever or with one or more severe constitutional/enteric symptom OR dysentery [[≥2 loose stools with gross blood (hemoccult positive) in 24 hours] AND [*oral temperature* ≥38.0°C OR ≥1 severe constitutional/enteric symptom]]. (Amended: 23 July 2019)
- Shedding of *S. sonnei* strain 53G.
 - Shedding of *S. sonnei* strain 53G is defined as positivity of at least one stool sample either by culture or qPCR or both.
- Severe diarrhea
- More severe diarrhea.
- Dysentery.

205626 (S SONNEI MONO GMMA SBVGH-003 [H03_03TP])
Protocol Amendment 6 Final

- Weight of all grade 3-5 stools.
- Total number of all grade 3-5 stools.
- Confirmed S. sonnei 53G shedding AND moderate or severe diarrhea OR dysentery OR presence of oral temperature ≥ 38.5 °C OR presence of one or more severe intestinal symptoms (abdominal pain, cramping, nausea, vomiting, gas, anorexia).
- Disease not fulfilling the protocol primary case definition for shigellosis associated or not with mild to moderate symptoms including: passing loose stool (not meeting the protocol definition of moderate or severe diarrhea), abdominal pain, abdominal cramps, gas, anorexia, nausea, headache, myalgia, malaise, arthralgia, fever, vomiting and IV fluid administration.
- Time to onset of shigellosis after challenge, according to the protocol primary case definition.

Safety

Solicited adverse events

• Occurrence of each solicited local and systemic adverse event within 7 days after each vaccination.

Unsolicited adverse events

• Occurrence of unsolicited AEs within 28 days after vaccination and after challenge, according to Medical Dictionary for Regulatory Activities (MedDRA) classification.

Serious adverse events

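### Every primary case needs proven shedding, but no culture/qPCR specimen is required before early antibiotics: a narrow, cheaply closed route to missed cases

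*Protocol*

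**What the plan says.** - **Case definition (Section 4.3).** A primary case is shedding "accompanied by moderate or severe diarrhea OR shedding with an oral temperature of" at least 38.5°C. Shedding is needed in both branches.
- **Shedding (Section 11.2).** It "is defined as positivity of at least one stool sample either by culture or qPCR or both", measured from Day 57 to Day 64.
- **Which stool is tested (Section 3.2).** "The first stool sample collected during a 24 hour period on the day after challenge agent administration (from 00:01 to 24:00") goes to culture and qPCR. If no stool is produced by midnight, a rectal swab is taken. Two stools are collected on Day 64. All stools passed are collected and inspected.
- **How often (Table 4, footnote 8).** "Sampling to be done daily during inpatient stay". Section 6.6.10.3 refers culture and qPCR to the timepoints in Table 4: "Aliquots of stool will be collected for fecal sIgA, inflammatory response, culture and qPCR, at each predefined timepoint (see Table 4").
- **Early antibiotics (Section 3.2).** "Subjects may be treated with antibiotics before the 5th day after challenge (Day 62) if" any of three conditions is met, one of them being physician judgment. No stool or swab for culture or qPCR is required before the first dose. Early-treated subjects stay on the unit until the planned discharge on Day 65.
- **Severe diarrhea (Section 4.1).** Bringing antibiotic treatment forward before the 5th day after challenge counts as a medical intervention in this definition.

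**The concern.** The tested stool is fixed by its order in the day. The decision to treat early is driven by illness and can come at any hour. If the first stool of a day is negative and the subject falls ill and starts antibiotics later that day, the next designated specimen comes after treatment has begun. The diarrheal stools passed just before the first dose are in hand but are not designated for testing.

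Under Section 4.1, early treatment can itself place a subject in the severe diarrhea category. For such a subject the clinical part of the case definition may be met, and shedding alone then decides case status. If shedding is never documented, a clearly ill subject becomes a primary non-case. The shedding endpoint and the composite that requires confirmed shedding would be affected in the same way. The trial is sized on 21 cases, so a few lost confirmations would matter.

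**Working it through.** **1. The plan's own figures (Section 11.4) reproduce.** Inputs: true VE 70%, placebo attack rate 58%, one-sided alpha 5%, power 80%, 22% non-evaluable.
- Share of cases in the vaccine arm under VE 70%: 0.3/1.3 = 0.2308, against 0.5 under no effect.
- With 21 cases, reject if 6 or fewer are in the vaccine arm: exact alpha 0.039, power 0.808.
- Evaluable per arm: 21/(0.58 × 1.3) = 27.9, so 28. Enrolled per arm: 28/0.78 = 35.9, so 36, or 72 in total.

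**2. What must happen for a case to be lost.** All of these together:
- every designated sample before treatment is negative by culture and by qPCR;
- illness begins after that day's first stool, and the first antibiotic dose is given before another designated stool;
- every sample after treatment, through Day 64, is also negative by both assays.

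A single positive at any point breaks the chain. If illness starts with the day's first stool, that stool is the tested one and would normally precede treatment.

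**3. Weight of one lost case.** Expected placebo cases: 28 × 0.58 = 16.24. Expected vaccine cases: 28 × 0.174 = 4.87. One placebo case is 1/16.24 = 6.2% of that arm's cases. Losing one on placebo only gives apparent VE = 1 − 4.87/15.24 = 68.0%.

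**4. Sensitivity to an assumed loss.** The protocol gives neither the share treated early nor the share of those never confirmed, so the losses below are assumptions. Apparent VE = 1 − 0.174(1 − b)/[0.58(1 − a)], where a and b are the fractions of placebo and vaccine cases lost. Power is by full enumeration with 28 per arm. Section 11.8 does not name the interval method, so two are shown: a 90% log risk-ratio interval (0.5 added when the vaccine count is zero), and the conditional exact test that matches the sizing in Section 11.4.

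| Loss, placebo / vaccine | Placebo rate | Apparent VE | Power, log risk ratio | Power, conditional exact |
|---|---|---|---|---|
| 0 / 0 | 58.0% | 70.0% | 0.935 | 0.82 |
| 5% / 0 | 55.1% | 68.4% | 0.90 | 0.77 |
| 10% / 0 | 52.2% | 66.7% | 0.86 | 0.70 |
| 15% / 0 | 49.3% | 64.7% | 0.80 | 0.63 |
| 5% / 5% | 55.1% | 70.0% | 0.92 | 0.80 |
| 10% / 10% | 52.2% | 70.0% | 0.895 | 0.77 |
| 15% / 15% | 49.3% | 70.0% | 0.87 | 0.73 |

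Equal proportional loss leaves VE unbiased and costs only power. Bias appears only when the proportions differ. When placebo loses more, VE is understated.

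**The case against.** **The route is narrow.** This stands. Either assay suffices, early-treated subjects remain in daily sampling, and swabs cover days without a stool.

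**Antibiotics are not shown to abolish shedding.** A reader might infer that they do from Section 1.3.1: "Administration of an effective antibiotic will significantly reduce, or eliminate, symptoms within 24 hours of initiation". That sentence concerns symptoms, not excretion of the organism or its DNA. Section 3.2 provides for subjects still shedding 48 hours after ciprofloxacin is started. The documents therefore do not support the view that a subject treated before a first positive will generally stay negative.

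**The 58% may already contain the loss.** Section 11.4 gives it as the rate for this trial's primary definition, in the same challenge model and at the same 1500 CFU. The model's sampling schedule is not given, so the overlap can be neither confirmed nor excluded. The table may therefore deduct something already counted.

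**Loss mainly on placebo is an inference.** If the vaccine works, more placebo cases would be lost in number, but bias needs a larger proportion lost. A loss of 5–15% on placebo and none on vaccine has no source in the protocol. Greater loss on placebo would work against the vaccine, not toward a false success.

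**Testing on one day only.** Read alone, the Section 3.2 sentence might suggest that only the day after challenge is tested. The sampling schedule in Section 3 and Table 4 make clear that it is daily.

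**Other safeguards.** The two secondary shigellosis definitions and more severe shigellosis need no shedding, so such subjects can still count there. That does not restore the primary endpoint. The Study Procedures Manual, not shown, may give further sampling detail, but the protocol itself fixes the tested stool. No later analysis can supply a result for a specimen that was not tested.

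**Conclusion.** The gap is real and small. Shedding is required for every primary case, one stool per 24-hour period is designated for testing, and nothing secures a specimen before early antibiotics. A case can be lost through this gap only if every sample from Day 57 to Day 64 is negative by both assays. How often that would happen cannot be derived from the protocol.

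If it happens, each lost placebo case is about 6% of the roughly 16 expected. Losing that fraction on placebo alone would lower apparent VE by about 2 points and conditional exact power from 0.82 to about 0.75 (log risk-ratio interval: 0.935 to about 0.89). These figures assume 28 evaluable per arm, true VE of 70% and a 58% rate that does not already include such losses. Bias toward zero is possible but not established. This is a worthwhile low-cost improvement in case ascertainment, not an error that undermines the primary analysis.

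**What to change.** In Section 3.2, with Section 6.6.10.3 and Table 4 aligned, add one event-driven specimen. For any subject starting antibiotics before Day 62, also test by culture and qPCR the last stool already collected before the first dose, or a rectal swab if there is none. State that this result counts toward the shedding definition. State also that treatment is not delayed for it and that the treatment criteria are unchanged.

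Cost: one extra culture and qPCR per early-treated subject, usually on stool already in hand.

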6.6.11. Study vaccine/placebo administration

- After completing all prerequisite procedures prior to vaccination, one dose of study vaccine or placebo will be administered IM preferably in the deltoid of the non-dominant arm (refer to Section 7 for detailed description of the vaccine/placebo administration procedure). If the investigator or delegate determines that the subject's health on the day of administration temporarily precludes vaccine/placebo administration, the visit will be rescheduled within the allowed interval for this visit (refer to Table 5).
- The subjects will be observed closely for at least 30 minutes following the administration of the vaccine/placebo, with appropriate medical treatment readily available in case of anaphylaxis.

6.6.12. Challenge administration and inpatient stay

- After completing all prerequisite procedures prior to challenge, one challenge dose of S. sonnei 53G will be administered. If the investigator or delegate determines that the subject's health on the day of administration precludes challenge administration, the challenge agent will not be administrated to the subject.
- The subjects will be observed closely for the entire period of the inpatient stay (9 days, from Day 57 to Day 65) following the administration of the challenge, with appropriate medical treatment readily available in case of need.

Refer to Section 3.2 and SPM for more details related to the preparation and administration of the challenge agent and the collection of samples during the inpatient stay.

6.6.13. Check and record concomitant medication/vaccination and intercurrent medical conditions

Concomitant medication/vaccination must be checked and recorded in the eCRF as described in Section 7.6.

Intercurrent medical conditions must be checked and recorded in the eCRF as described in Section 7.7.

6.6.14. Recording of AEs, SAEs, pregnancies and AESIs

- Refer to Section 9.3 for procedures for the investigator to record AEs, SAEs, pregnancies and AESIs. Refer to Section 9.4 for guidelines and how to report SAE, pregnancy and AESI reports to GSK Biologicals.
- The subjects will be instructed to contact the investigator immediately should they manifest any signs or symptoms they perceive as serious.

205626 (S SONNEI MONO GMMA SBVGH-003 [H03_03TP])
Protocol Amendment 6 Final

